## 5. Specification of the intended purpose of the device

Naevia Medical is a clinical decision support software (CDSS) that, based on clinical input data (history, symptoms, complementary test data...) of adult patients with heart disease, provides healthcare professionals with prioritized, justified and referenced recommendations and knowledge suggestions related to diagnosis and/or treatment (recommended tests, medications, interventions,..).

## 6. Intended target groups and user, indications, and contraindications

### Intended target groups

- Adult patients with valvular heart disease, offering diagnostic, prognostic and therapeutic recommendations.

### Intended users

Medical doctors or residents who are familiar with the user manual and how to use the tool.

### Indications

- Naevia medical is indicated, as part of the assessment of a patient by healthcare professionals, to assist in making diagnostic prognostic and therapeutic decisions of patients suffering from valvular heart disease.

### Contraindications

Population under 18 years of age.

Medical emergency situations.

## 7. Description of intended clinical benefits to patients. Clinical outcome parameters.

It is expected that, compared to conventional clinical management without a clinical decision support system, naevia will increase the number of appropriate recommendations and significantly reduce the number of inappropriate and absent recommendations in all the domains analyzed.

Dilemma Solutions S.L.	CHAPTER 06-1C	TD01-06-1C Ver.: 01 2025/03/03
	CLINICAL EVALUATION PLAN (CEP)	Page 12 of 38

## **7.1 Direct clinical benefit to provide healthcare professionals with recommendations and suggestions for knowledge related to diagnosis, prognosis and/or treatment**

- Positive impact on enhancing the ability of healthcare professionals to provide a greater number of recommendations appropriate to each patient's specific situation, supporting diagnostic and clinical decision making.

Naevia medical provides recommendations based on the latest evidence and clinical guidelines, supporting informed and updated decision-making. It promotes consistency in care by standardizing data presentation and encouraging evidence-based practice, reducing variability in patient treatment and clinical inertia. Additionally, the CDSS reduces medical errors by offering knowledge-based suggestions, particularly in high-pressure environments with complex patients, and serves as an educational tool, keeping professionals informed about scientific updates while they perform their clinical duties.

Naevia Medical has developed an advanced platform for managing clinical data, which has demonstrated its effectiveness, acceptability and usability in various studies. This platform has been key in COVID-19 research, especially in cardiac diseases such as cardiomyopathies and heart failure.

### Evidence from pre-clinical evaluation

- Through the system functions and features, users have to be able to get recommendations and suggestions for knowledge related to diagnosis, prognosis and/or treatment.
  - o V&V per EN ISO 62304 and install validation. All tests provide recommendations and suggestions and thus CDSS is verified by all tests.
  - o V&V per EN 82304 and install validation. All tests provide recommendations and suggestions and thus CDSS is verified by all tests.
  - o Usability testing of the software by representative users to successfully provides recommendations and suggestions for knowledge related to diagnosis, prognosis and/or treatment.
- Capability of Naevia medical in the management of patients with cardiovascular diseases: a pre-clinical study of simulated cases in patients with valvular heart disease, using the "2021 ESC/EACTS Guidelines for the management of valvular heart disease", must validate the Naevia medical's capability in the management of patients with valvular heart disease.

### Evidence from clinical evaluation/investigations

- Software enables to provide recommendations and suggestions for knowledge related to diagnosis, prognosis and/or treatment: scientific literature confirms that SW system functions and features are aligned with current user requirements as described in relevant publications and as included in the DUE.

Dilemma Solutions S.L.	CHAPTER 06-1C	TD01-06-1C Ver.: 01 2025/03/03
	CLINICAL EVALUATION PLAN (CEP)	Page 13 of 38

- Increase of appropriate recommendations: number of appropriate recommendations – an observational, single-centre study consisting on a clinical validation of a CDSS applied to retrospective clinical cases of cardiology patients with valvular heart disease, shall confirm an increase in the number of appropriate recommendations by by a factor of three over the recommendations generated with general management without the support system.
- Inappropriate recommendations: number of inappropriate recommendations – an observational, single-centre study consisting on a clinical validation of a CDSS applied to retrospective clinical cases of cardiology patients with valvular heart disease, shall confirm that naevia medical, compared to conventional management, is able to reduce the number of inappropriate and mising recommendations based on scientific evidence in the diagnostic and therapeutic areas.
- Concordance between expert evaluators:
  - o The analysis of the degree of agreement/disagreement in the different domains, evaluated using a Likert scale, analysed using ordinal regression (Joshi, Kale et al. 2015). Response options: 1. Strongly disagree, 2. Disagree, 3. Neither agree nor disagree, 4. Agree, 5. Strongly agree.
  - o The panel's agreement with the CDSS was very high, with a mean Likert scale score above 4 in all domains (STD: 4.53, LTD: 4.68, CMT: 4.58, ITI: 4.62). The probability of strongly agreeing was significantly higher than the probability any of the other categories (z.ratio (5|1)= 30.88, p-value< 0.001, z.ratio (5|2)= 31.67, p-value < 0.001, z.ratio (5|3) = 30.21, p-value< 0.001, z.ratio (5|4)= 22.54, p-value< 0.001).

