### Main clinical investigation

Title	Clinical validation study of naevia medical, a decision support tool for valvular heart disease
Registration number	ClinicalTrials.gov ID NCT06392464
Start and End	2024
Publication	Pending
Design	pre-test-post-test of a randomly assigned group, using a longitudinal repeated measures approach and retrospective validation
Duration	3 months
Centres	Instituto de Investigación Sanitaria de Santiago de Compostela (IDIS)
Sponsor	DILEMMA SOLUTIONS SL
Main objective	Demonstrate that the use of the naevia medical CDSS significantly increases appropriate recommendations based on clinical practice guidelines, and decreases the number of inappropriate recommendations received by the patient, compared to conventional management.
Device investigation under	Naevia medical
Number of participants	101

Dilemma Solutions S.L.	CHAPTER 06-1C CLINICAL EVALUATION PLAN (CEP)	TD01-06-1C Ver.: 01 2025/03/03
		Page 33 of 38

Title	Clinical validation study of naevia medical, a decision support tool for valvular heart disease	
Inclusion criteria	
Retrospective clinical retrospective cases of patients with valvular heart disease will be selected in a stratified randomised manner from among:
 
 
(i) patients presented at a medical-surgical session.
 
ii) patients from the monographic consultation of valvopathies.
 
 
Inclusion criteria:
 
 
- Clinical cases of patients randomly selected from among those presented during the year 2022 in medical-surgical session with the main diagnosis of aortic valvular stenosis, aortic insufficiency, mitral stenosis and mitral insufficiency (greater than moderate grade). Randomisation will be stratified ensuring that 50% come from the medical-surgical session.
 
- Clinical cases of patients randomly selected from clinical records of the Valvopathy Consultation seen in 2022 with the main diagnosis of aortic stenosis, aortic insufficiency, mitral stenosis and mitral insufficiency (major degree).
 
mitral regurgitation (greater than moderate grade). Randomisation will be stratified by ensuring that at least 40% of patients have aortic valve disease and 20% have mitral valve disease.
 
- Age <math>\geq 18</math> years.
 
	

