### Statistical analysis plan

The study is designed as a pre-test-post-test evaluation of a randomly assigned group, using a longitudinal repeated measures approach and retrospective validation. The clinical management of the included cases will be retrospectively evaluated by a panel of 3 experts with access to the most updated guidelines. For each case, the panel will perform the assessment at baseline (without CDSS) and repeated the assessment after the activation of the CDSS. The experts will label all the given clinical recommendations as appropriate or inappropriate and will identify the ones that are missing but relevant for clinical decision making. Finally, they will state their grade of agreement with the CDSS suggestions on a five-level Likert scale. The number and percentage of appropriate, inappropriate and missing relevant recommendations in each scenario will be considered for analysis.

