### **Analysis of the amount and quality of recommendations**

The impact of the CDSS activation on the recommendations will be assessed by analyzing the *number* of recommendations (appropriate, inappropriate, missing) per patient. The mean number of appropriate, inappropriate, and missing relevant recommendations generated per patient will be compared before and after the CDSS activation. Descriptive statistics, including mean (standard deviation [SD]), median (interquartile range [IQR]), and range, will be reported for these counts. To statistically compare the distributions of the *number* of appropriate, inappropriate, and missing recommendations per patient before and after CDSS implementation, the Wilcoxon signed-rank test will be applied.

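### The Likert agreement analysis names ordinal regression but no term for case or expert, so the precision behind its z-ratios cannot be judged and may be overstated (minor)

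*Protocol*

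**What the plan says.** - **Method.** Protocol section 7.1 (Evidence from clinical evaluation/investigations, concordance item) gives the whole method in one phrase: agreement is "evaluated using a Likert scale, analysed using ordinal regression". It mentions no random effect, clustered variance or rater term.
- **Results.** The same item reports domain means of "STD: 4.53, LTD: 4.68, CMT: 4.58, ITI: 4.62" and contrasts of category 5 with each other category: "z.ratio (5|1)= 30.88, p-value< 0.001, z.ratio (5|2)= 31.67, p-value < 0.001, z.ratio (5|3) = 30.21, p-value< 0.001, z.ratio (5|4)= 22.54". Table 1 in section 11 repeats them among the parameters on which benefit-risk acceptability depends. Neither place gives a standard error, an interval or the number of ratings.
- **Design.** Section 14 (Main clinical investigation) gives 101 participants and describes a design "using a longitudinal repeated measures approach and retrospective validation". It attaches no correlation structure to the Likert model.
- **Raters.** In the SAP, cases are "retrospectively evaluated by a panel of 3 experts with access to the most updated guidelines", and the experts also give a five-level agreement rating. The SAP does not say whether this is one panel rating or three individual ratings, or whether it is given per case, per domain or per recommendation.
- **SAP analysis.** The only test named is for the recommendation counts ("the Wilcoxon signed-rank test will be applied"). The SAP has no analysis for the Likert ratings.

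**The concern.** Ratings of four domains on one case share the same patient, the same record and the same assessors. If each expert rated separately, there are further repeats within case and within expert. Such ratings are usually positively correlated. An ordinal regression that takes each rating as an independent observation then gives standard errors that are too small, z-ratios that are too large and p-values that overstate the evidence.

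Because the plan gives neither the number of ratings nor the handling of repeats, a reader cannot tell whether this happened. What is at stake is the stated strength of a supporting result in Table 1. The main objective, which concerns recommendation counts, is not affected.

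**Working it through.** **Inputs from the documents.** z-ratios 30.88, 31.67, 30.21 and 22.54; domain means 4.53, 4.68, 4.58 and 4.62; 101 cases; 3 experts. Average mean = (4.53 + 4.68 + 4.58 + 4.62)/4 = 4.6025.

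**Assumptions.** The Likert figures come from the 101-case study, the domains carry equal numbers of ratings, and the contrasts behave like simple multinomial ones.

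**Step 1: how many independent ratings would give these z-ratios?** With N independent ratings and category proportions p1 to p5,

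z(5|k) = (p5 − pk) / √{[p5 + pk − (p5 − pk)²] / N}.

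For each N, the four z-ratios and the constraint that the proportions sum to 1 determine p1 to p5, and hence an implied mean:

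| N | Would correspond to | Implied mean |
|---|---|---|
| 101 | one rating per case | 4.875 |
| 303 | 3 experts × 101 | 4.676 |
| 404 | 4 domains × 101 | 4.596 |
| 606 | – | 4.463 |
| 1,212 | 4 × 3 × 101 | 4.195 |

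The reported 4.6025 corresponds to N ≈ 396 (389 to 402 when rounding of the domain means is allowed for), which is 2.0% below 404. At N = 404 all four z-ratios are reproduced with p1 to p5 of about 0.035, 0.031, 0.038, 0.095 and 0.801.

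**Step 2: what this does and does not identify.** Adding the mean gives five equations in five unknowns once the proportions are tied to sum to 1. A solution is therefore expected and is no test of independence: 396 is an *effective* number of ratings. With 1,212 individual ratings and clustering allowed for, the same effective number arises at

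design effect = 1,212/396 = 3.06, so ICC = (3.06 − 1)/(12 − 1) ≈ 0.19.

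A simulation of 101 cases with 12 ratings each, case-clustered standard errors and a latent-scale ICC of 0.41 gave z-ratios of about 30.4, 31.4, 30.4 and 23.5, close to those reported.

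**Step 3: size of the effect if about 404 ratings were treated as independent.** With 4 ratings per case, design effect = 1 + 3 × ICC, and z is overstated by its square root. The documents give no ICC, so a range is assumed:

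| ICC | Design effect | Overstatement of z | Corrected z (5 v 1, 2, 3, 4) |
|---|---|---|---|
| 0 | 1.0 | 1.00 | 30.9, 31.7, 30.2, 22.5 |
| 0.2 | 1.6 | 1.26 | 24.4, 25.0, 23.9, 17.8 |
| 0.5 | 2.5 | 1.58 | 19.5, 20.0, 19.1, 14.3 |
| 1.0 | 4.0 | 2.00 | 15.4, 15.8, 15.1, 11.3 |

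All remain p < 0.001. The ICC here is on the scale of the observed ratings. In simulation with 4 ratings per case, a latent-scale ICC of 0.23 gave overstatements of 1.12 to 1.15, and one of 0.55 gave 1.29 to 1.42.

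**The case against.** The strongest reply is that nothing in the documents says the ratings were treated as independent. Ordinal regression includes mixed and cluster-robust forms, the design is described as repeated measures, and section 14 points to a separate investigation plan that may hold the detail. This reply stands. A reader might infer from the match with 404 that independence was assumed, that the standard errors are demonstrably too small, or that the panel gave one consensus rating per domain. The documents support none of these as fact, because a clustered analysis of 1,212 individual ratings fits about as well.

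Two further points stand:

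- No intervals are reported, so none can be called too narrow. If there is one panel rating per case and domain, each domain mean comes from different cases, and correlation between domains does not affect its precision.
- The reported finding of a mean above 4 in every domain is a statement about point estimates, which clustering does not move.

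The reply does not remove the gap. Followed literally, the stated method gives wrong standard errors whenever ratings on one case are correlated. If a clustered method was used, it is described in neither document.

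**Conclusion.** The concern holds as a minor point about specification and precision. The plan names a model for repeated ratings without a case or expert term, the SAP has no Likert analysis, and the rating unit and number of ratings are not stated. The published figures are consistent with about 404 ratings treated as independent, but do not prove it.

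On that reading, z is overstated 1.26 to 1.58 times for an assumed within-case correlation of 0.2 to 0.5, and by no more than 2 times. It would be tempting to conclude that the agreement result is unsound. The figures do not support this: even in the worst case the smallest z is 11.3, so strongly agree remains the most frequent category. Only the stated strength of evidence is in doubt. Confidence is high that the specification is missing and only moderate that independence was assumed. The size rests on the assumptions listed with the calculation.

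**What to change.** In Protocol section 7.1, in Table 1 of section 11 and in the SAP:

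1. State the rating unit (case, domain or recommendation; panel or individual) and the numbers of ratings, cases and experts.
2. Specify a cumulative-link mixed model with a random intercept for case, plus an expert term if ratings are individual. A bootstrap that resamples whole cases is an alternative. With only three experts, a fixed expert term is the simpler choice.
3. Replace the four z-ratios with the proportion of ratings in each agreement category, overall and by domain, with case-clustered 95% intervals. If the mixed model is used, average the proportions over the random effects so that they describe the whole set of cases.

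Proportions would also show what the z-ratios hide. At N = 404, the solution above implies about 80% strongly agree and about 6.6% (3.5% + 3.1%) in the two disagreement categories. These are inferred figures that the sponsor can confirm or correct.

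The cost is one re-run on existing data and a paragraph in the SAP. The downside is wider intervals than an independence analysis would give.

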#### Evidence from registries

Additionally, Naevia Medical's platform has been or is being used in other significant registries, such as:

- The “REDMIO20: Spanish Registry of Dilated Cardiomyopathy due to RBM20 Gene Mutation,” a multicenter registry coordinated by [name] from the Salamanca University Assistance Complex, which included 168 cases up to December 11, 2023.
- The “PROCeso asistencial integrado de Estenosis Aórtica grave Sintomática (PROCEAS)” 2020/405 registry, led by [name] from the Santiago de Compostela University Clinical Hospital, with 991 cases of aortic stenosis registered up to December 11, 2023.

Dilemma Solutions S.L.	CHAPTER 06-1C	TD01-06-1C Ver.: 01 2025/03/03
	CLINICAL EVALUATION PLAN (CEP)	Page 14 of 38

Evidence from post-market surveillance:

- PMS evidence to evaluate the absence of complications and low incidence of adverse events.
- Recommendations that could lead to a serious adverse event shall be identified as patient safety risks, including:
  - o Possibility of death.
  - o The need for a medical or surgical intervention that would not otherwise be necessary.
  - o Omission of critical recommendations that could adversely affect the patient's prognosis.

## **8. Alternative options for treatment, diagnostic and/or management**

The alternative to CDSS is conventional clinical management, where doctors alone face complex patients with limited decision time, contributing to medical errors (Newman-Toker, Nassery et al. 2023) (Makary and Daniel 2016). CDSS can reduce errors caused by oversight (Avery, Sheehan et al. 2021), but medical decisions still depend on doctors' experience, leading to avoidable harm and costs (Makary and Daniel 2016, 2017, Avery, Sheehan et al. 2021) (Bates and Gawande 2003, Shrunk, Rogstad and Parekh 2019).

Many patients do not receive the benefits of scientific medical recommendations (Ghazi, Yamamoto et al. 2022, Bhatt, Varshney et al. 2023), despite the increase in health record data and new clinical guidelines (Balas and Boren 2000, Obermeyer and Lee 2017). Limited consultation time, patient complexity, and provider inexperience increase care variability (Singh and Sittig 2015, Jarjour, Henri et al. 2020).

Medical progress relies on doctors' decisions and patient adherence (Walewska-Zielecka, Religioni et al. 2021, Fonarow, Yancy et al. 2011). However, doctors often use heuristics—mental shortcuts that speed decisions but cause cognitive biases (Blumenthal-Barby and Krieger 2015). These biases, influenced by past experiences, clinical inertia, and patient factors like age or sex, affect decision accuracy (Blumenthal-Barby and Krieger 2015).

## **9. Clinical Evaluation Strategy – Relevant clinical data and information about the state of the art – Sources and strategies to locate data. Methods to be used to assess data.**

### **9.1 Outline of the clinical evaluation strategy following Article 61 MDR**

Naevia medical is a Class IIa medical device software.

Following Article 61(3) of the MDR, the clinical evaluation is based on:

- (a) A critical evaluation of the relevant scientific literature currently available relating to the safety, performance, design characteristics and intended purpose of the device, meeting the following conditions as described in the clinical evaluation report:

Dilemma Solutions S.L.	CHAPTER 06-1C	TD01-06-1C Ver.: 01 2025/03/03
	CLINICAL EVALUATION PLAN (CEP)	Page 15 of 38

- It is demonstrated that this generation of Naevia medical subject to clinical evaluation for the intended purpose is potentially equivalent to the device to which the data relate, in accordance with Section 3 of Annex XIV, and
- It is shown that the data adequately demonstrate compliance with the relevant GSFRs.

(b) A critical evaluation of the results of all available clinical investigations, taking duly into consideration whether the investigations were performed under Articles 62 to 80 MDR, and acts adopted pursuant to Article 81 MDR, and Annex XV, and

(c) A consideration of the currently available alternative treatment options for the same intended purpose.

Moreover, Article 61(4) of the MDR, in the case of implantable devices and class III devices, clinical investigations shall be performed, except if:

- the device has been designed by modifications of a device already marketed by the same manufacturer,
- the modified device has been demonstrated by the manufacturer to be equivalent to the marketed device, in accordance with Section 3 of Annex XIV and this demonstration has been endorsed by the notified body, and
- the clinical evaluation of the marketed device is sufficient to demonstrate conformity of the modified device with the relevant safety and performance requirements.

This consideration enables a clinical evaluation strategy with the requirement to not perform specific pre-market clinical investigations with the DUE with the condition that clinical data provided from the equivalent device is sufficient and clinical evidence is available.

Per Article 2(48) MDR, 'clinical data' means:

Any information concerning the safety or performance that is generated from the use of a device and is sourced from the following:

- Clinical investigation(s) of the device concerned,
- Clinical investigation(s) or other studies reported in scientific literature, of a device for which equivalence to the device in question can be demonstrated,
- Reports published in peer reviewed scientific literature on other clinical experience of either the device in question or a device for which equivalence to the device in question can be demonstrated,
- Clinically relevant information coming from post-market surveillance, in particular the post-market clinical follow-up.

Clinical data are sourced from clinical investigations of the DUE to support its specific clinical performance aspects.

Dilemma Solutions S.L.	CHAPTER 06-1C	TD01-06-1C Ver.: 01 2025/03/03
	CLINICAL EVALUATION PLAN (CEP)	Page 16 of 38

In addition, despite meeting the regulatory definition of 'clinical data' through undergoing a clinical investigation with the device concerned, other sources of relevant information are considered, specifically pre-clinical data related to the DUE itself together with data pertaining to similar devices, to establish the current state of the art along with the criteria for the assessment of the safety and performance of this type of device. Data concerning similar devices and current alternatives are considered as supporting data and to enable planning of PMS and PMCF activities.

The scientific quality of the available datasets is assessed during the appraisal stage of the clinical evaluation. Appraised datasets that qualify as 'clinical data' (as defined in Article 2 (48) of the MDR) are included in the analysis to determine if the available information provides sufficient clinical evidence.

